1.3 Research questions

The present study aims to respond the following research questions (RQ).

- 1. Is there any difference between the game performance of older adults with typical cognition and individuals with MCI?
- 2. What is the concurrent validity of the game-based screening for MCI detection?
 - 2.1 Is there any relationship between game performance and total score of traditional cognitive tests (MoCA score and Quick MCI (Qmci)) in older adults with typical cognitive and older adults with MCI?
 - 2.2 Is there any relationship between the sub-MoCA scores and sub-Qmci scores and the game metrics in older adults with typical cognitive and older adults with MCI?

- 3. What is the diagnostic accuracy of the game-based screening assessed by sensitivity, specificity, accuracy, and the Area Under Curve (AUC) of the game-based screening for MCI detection?
- 4. Is game performance an associated factor with cognitive status controlled by demographic variables?
- 5. Is there any difference between the level of state anxiety while playing the G3 game and while administering traditional cognitive tests in older adults with typical cognition and individuals with MCI?
- 6. What is the usability of the G3 as a game-based screening?

2. Literature review

This chapter will address several key areas essential for understanding the use of SCGs in cognitive screening for MCI. It will begin with an overview of cognitive functions and their domains, followed by a discussion of MCI, its prevalence, and associated brain changes. The review will then examine cognitive changes with aging and MCI, traditional cognitive tests used for MCI diagnosis, and their limitations. It will explore digital technologies for MCI screening, focusing on the potential of SCGs. Finally, the chapter will highlight research gaps and propose directions future studies, emphasizing the investigation of the G3, a SCG designed for older adults, for MCI detection.

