to examining the relationship between game performance and cognitive status, requiring a moderate number of participants. Thus, this study, designed with a statistical power of 0.8, an alpha level of 0.05, and a medium effect size of 0.7, requires a minimum sample size of 58 participants. Twenty-nine older adults (65 and above) who meet the diagnostic criteria for MCI, and 29 older adults with typical cognition will be eligible to participate in the study. Other reasons for justifying the sample size include: 1) The statistical analyses to answer questions that aim to compare two conditions, or two groups requires a smaller sample size; and this small sample size is insufficient to justify correlational analysis. 2) the "Events Per Variable" (EPV) rule is often used in statistical modeling, particularly in logistic regression, to determine the minimum sample size needed to ensure reliable and valid results. The general rule is to have at least 10 events (outcomes of interest) for each predictor variable (151). Therefore, using regression analysis to explore the six associated factors (game performance, age, sex, educational level, tech savviness, and living status) with the presence of MCI would necessitate 60 events (instances of the outcome of interest). Assuming an equal distribution of events and non-events, at least 120 participants would be needed in total to achieve 60 events, ensuring that each predictor variable is adequately supported by the data and enhancing the reliability of the statistical model. However, for a feasibility study involving a brand-new, untested test, it is not ethical to recruit a large sample size and burden vulnerable older adults with participation. Besides, at this point of the study, it is not known how many independent variables will be included in the model and that depends on the results of the factorial analysis that precedes the logistic model. Therefore, I aim to treat the research about the associated factors with the presence of MCI (RQ4) as a pilot to gather preliminary data. This approach can help refine the research design and hypotheses, and the results can be used to justify the need for a larger study

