Finally, the ROC curve will be calculated and plotted. TPR and FPR need to be calculated for various threshold values. Then, TPR (y-axis) against FPR (x-axis) for each threshold will be plotted. The closer the ROC curve is to the upper left corner, the higher the test's accuracy, as this position represents a sensitivity of 1 and a false positive rate of 0 (specificity of 1). An ideal ROC curve has an AUC of 1.0. An AUC of 0.5 indicates no discrimination, 0.7 to 0.8 is acceptable, 0.8 to 0.9 is excellent, and above 0.9 is considered outstanding (155,156).

To investigate if the game performance is an associated factor with cognitive status controlled by demographic variables (RQ4), logistic regression analysis (157) will be used. For all variables, categories will be combined into broader categories, when possible, to improve the power of the logistic regression model (158). Chi-Square test will be used to determine if there is a significant

association between variables and cognitive status. Principal Component Analysis (PCA) will be used to reduce the number of variables in a dataset while preserving as much variability (information) as possible (159). To determines which factors to retain based on explained variance, and Eigenvalue Cut-Off of 1 will be applied. Following this, logistic regression model will be run with the included variables. The performance of the logistic regression model with be evaluated using ROC analysis and test characteristics (160).

To compare the differences between the level of anxiety while playing the game and while traditional cognitive tests in older adults with typical cognition and with MCI (RQ5), either the Paired t-test or Wilcoxon Signed-Ranks test (155) will be used as appropriate, with an α level of 0.05, to compare the anxiety level in the two conditions- while playing the games and while performing MoCA. If the mean difference is significant and lower while playing the game compared with MoCA and Qmci, it means that the G3 causes less anxiety compared to the traditional cognitive screening tools.

To explore the usability of the game-based screening (RQ6), the SUS results will be calculated and interpreted as follows:

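### RQ4 does not secure a game effect adjusted for demographics: the PCA before the logistic model is not limited to the game metrics, and no demographic is held in the model

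*Protocol*

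**What the plan says.** Protocol section 1.3 poses RQ4: "Is game performance an associated factor with cognitive status controlled by demographic variables". Section 3.9 answers it with logistic regression and then lists preparatory steps. Categories are merged where possible, and variables are tested against cognitive status by chi-square. Then comes the reduction step: "Principal Component Analysis (PCA) will be used to reduce the number of variables in a dataset while preserving as much variability (information) as possible". The retention rule is "To determines which factors to retain based on explained variance, and Eigenvalue Cut-Off of 1 will be applied". Finally, "Following this, logistic regression model will be run with the included variables".

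Section 3.3 lists the candidates for this model as game performance and five demographics (age, sex, education, technology savviness, living status). It says the number of independent variables is not yet known and "depends on the results of the factorial analysis that precedes the logistic model". It adds that a simpler model with only the strongest predictors will be used, and it calls RQ4 a pilot.

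The protocol does not state which variables enter the PCA, whether component scores or original variables enter the logistic model, or that any demographic stays in the model whatever the earlier steps show.

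**The concern.** An adjusted association needs the exposure and the covariates as separate terms in one model. A PCA over both sets gives components that are weighted sums of both. The coefficient of a component dominated by game metrics then carries part of the age and education effects and cannot be read as the game effect given demographics.

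Confounding is to be expected here. Section 2.2.1 names age and lower education as risk factors for MCI. Section 2.3.5 cites correlations of game completion time with age (0.2 and 0.24) and with education (-0.3 and -0.23). No matching of the groups on either is planned. Section 1.2 gives the neglect of demographics in earlier work as a reason for the study, and section 3.3 says the RQ4 result can be used to justify a larger one. A confounded component reported as an adjusted association would mislead that decision.

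**Working it through.** **1. The plan's own figure.** Section 3.3 uses 10 events per predictor and six predictors: 10 x 6 = 60 events, and 60 / 0.5 = 120 participants at an equal split. This reproduces. With the planned 29 MCI cases there are 29 / 6 = 4.8 events per predictor. If the six game metrics of section 3.6 and the five demographics all entered, it would be 29 / 11 = 2.6. At 10 events each, 29 / 10 = 2.9, so two predictors are supported and nearly three. Some reduction is needed; the question is which variables it acts on.

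**2. Possible readings of the text.**
- *PCA over all candidates.* Section 3.9 sets no limit on the inputs. Section 3.3 already counts game performance as one of six factors and lets the PCA decide how many predictors remain. A PCA on game metrics alone would not shorten that list.
- *PCA on the game metrics only.* This is possible, because game performance is one factor measured by six metrics.
- *Selection of original variables.* The final model is run on the included variables, which may be originals that survive the chi-square, PCA and strongest-predictor steps.

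**3. Reading one, first simulation.** Assumptions: 2000 datasets of 58; six metrics driven by one game ability, two of them dichotomised; ability depends on age, education and technology with coefficients of 0.2 to 0.25 in size; MCI depends on age and education but not on ability. Results:
- PCA over all 11 variables kept 3.4 components on average.
- At least one component loaded above 0.3 on both a game metric and a demographic in over 99% of datasets.
- Demographics made up 21% of the squared loadings of the game component.
- That component was significant at 5% in 35% of datasets.
- The first component of the six metrics, with the five demographics as separate covariates, was significant in 6%.

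**4. Reading one, by size of group difference.** Assumptions: 29 v 29; the groups differ by the stated amount in both age and education; slopes of the metrics on them are close to the cited correlations; no other game-MCI link. The ranges cover four assumed strengths of correlation among the metrics, with 500 datasets each.

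| Assumed difference (SD) | First component, PCA over all variables |
|---|---|
| 0 | 4-5% |
| 0.2 | 7-13% |
| 0.3 | 11-22% |
| 0.5 | 27-55% |

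PCA on the game metrics with age and education entered separately stayed at about 5-6%. The Monte Carlo standard error at 5% is sqrt(0.05 x 0.95 / 500) = 1.0 percentage point. At 40% it is sqrt(0.4 x 0.6 / 500) = 2.2 points. The excess vanishes when the groups do not differ, so it is confounding.

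If the PCA is run literally on the six listed factors (one game score and five demographics), the component loading most on the game score was significant in 56% of datasets at 0.5 SD.

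**5. Selection reading.** A univariate screen at p < 0.05 dropped age or education in 77% of datasets at 0.5 SD. The false-positive rate for game performance stayed near 5%, so the harm on this reading is loss of the stated control rather than false positives.

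**The case against.** The strongest reply is that the protocol never names the PCA inputs. The wording is a generic description of the method, and the game-only reading fits the fact that one factor is measured by six metrics. On that reading the adjusted association can be estimated. This stands. A reader might infer that the protocol plans to blend game metrics and demographics, so that the adjusted effect cannot be estimated at all; the documents do not support that as a statement of fact. They support only that nothing prevents it, and that section 3.3 points towards it.

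The input list might also be left to a statistical analysis plan. That answers only part of the point. The protocol itself fixes the PCA, the eigenvalue rule, the dependence of model size on it and the strongest-predictor step. Together these conflict with a promise to control for demographics.

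The size rests on assumptions. The protocol gives no expected age or education difference between groups, and the cited correlations concern completion time only. No single false-positive rate should be quoted as the plan's. It would likewise be wrong to say that the eigenvalue rule keeps about 5 of 11 components here. That figure (5.1) comes from pure noise, and with correlated metrics about 3.1 to 4.3 are kept.

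Two facts lower the consequence. RQ4 is a declared pilot, and for RQ1 section 3.9 plans a MANCOVA with demographics as covariates, which compares game performance between groups without PCA. Neither repairs RQ4. The pilot label excuses imprecision but not a coefficient that answers another question.

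**Conclusion.** The point holds in conditional form. As written, section 3.9 does not restrict the PCA to the game metrics and does not keep demographics in the logistic model, so the adjusted association that RQ4 asks for is not secured. On the natural reading the game component's false-positive rate is about 5% with no group difference in age and education, 11-22% at 0.3 SD and 27-55% at 0.5 SD, against about 5-6% with separated terms. All these differences are assumed, with no true game-MCI link beyond demographics. On the selection reading demographics can drop out. On the game-only reading the PCA does no harm, but nothing then protects the demographics from the chi-square and strongest-predictor steps. Severity is moderate, given the pilot status of RQ4.

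**What to change.** In section 3.9 (RQ4), and in the matching sentences of section 3.3:
- Restrict the PCA to the game metrics. Use a method suited to the two binary metrics (completion, budget), or leave those two out of the score. Take one component as the game-performance score.
- Enter a short prespecified set of demographics as themselves, at least age and education. They are not to be chosen by the eigenvalue rule, the chi-square screen or the strongest-predictor step.
- Report the odds ratio of the game score with a 95% confidence interval, with and without the demographics, labelled as pilot.

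The cost is protocol wording and a few lines of code, with no extra participants or data. There is one small downside: 29 events support only two or three predictors, so sex, technology savviness and living status would move to sensitivity analyses.

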in the future. Additionally, based on the data, a simpler model with only the strongest predictors will be used to produce a more reliable regression model. Thus, for an initial study on a new test, correlational analysis is the most practical choice, allowing us to assess concurrent validity without requiring an excessively large sample size.

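### RQ4: the logistic model is built and scored by ROC on the same 29 + 29 participants, so its AUC, sensitivity and specificity are biased upward as the plan stands

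*Protocol*

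**What the plan says.** Protocol section 3.9 sets out the RQ4 analysis in this order: merge categories where possible, test each variable against cognitive status by chi-square, reduce the variables by PCA with an eigenvalue cut-off of 1, and fit a logistic regression. It ends: "The performance of the logistic regression model with be evaluated using ROC analysis and test characteristics".

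Section 3.3 adds that, depending on the data, "a simpler model with only the strongest predictors will be used to produce a more reliable regression model". The candidates there are "six associated factors (game performance, age, sex, educational level, tech savviness, and living status"), with game performance counted as one factor. The same section says that the final number of predictors is not yet known and will depend on the factor analysis.

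The only sample is "Twenty-nine older adults (65 and above) who meet the diagnostic criteria for MCI, and 29 older adults with typical cognition"; section 3.11 says approximately 60. Section 3.3 works out that six predictors would need 60 events and 120 participants, and therefore treats RQ4 as a pilot whose results may justify a larger study.

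The verbal AUC scale, "0.7 to 0.8 is acceptable, 0.8 to 0.9 is excellent", closes the RQ3 part of section 3.9. It is not repeated for RQ4.

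**The concern.** A fitted model separates the people it was fitted to better than it separates new people, because its weights have followed the chance features of those people. The effect grows with the number of terms per event, and grows again when predictors are chosen for their strength in the same data. RQ4 has few events, a predictor count that is not fixed, and a stated choice of the strongest predictors. Section 3.9 then names an ROC evaluation and no step that would remove the optimism.

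At stake is how RQ4 is read. Its stated use is to help justify a larger study. An apparent AUC in the 0.7s could be taken as support for the model when it would perform appreciably worse, or no better than chance, in new participants.

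**Working it through.** **Inputs (protocol section 3.3).** 58 participants, 29 events and 29 non-events; six listed factors; 10 events per predictor. From section 3.9: PCA eigenvalue cut-off of 1, and AUC 0.70 and 0.80 as grade boundaries (stated under RQ3).

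**The plan's own figure.** Events needed = 6 × 10 = 60; participants = 60 / 0.5 = 120. This reproduces. With 29 events the ratio is 29 / 6 = 4.8 per predictor, and the rule of 10 would allow 29 / 10 = 2.9, that is, two predictors.

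**Null simulation.** Data sets of 29 v 29 were generated with predictors unrelated to group. A maximum-likelihood logistic model was fitted and scored on the same 58 people, with AUC = (R₁ − n₁(n₁ + 1)/2) / (n₁n₀), where R₁ is the rank sum of the fitted scores in the MCI group and n₁ = n₀ = 29. The true AUC is 0.50. With independent normal predictors, fixed in advance, 4000 runs each:

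| Predictors | Mean apparent AUC | AUC ≥ 0.70 | AUC ≥ 0.80 |
|---|---|---|---|
| 2 | 0.59 | 3% | 0.1% |
| 3 | 0.62 | 7% | 0.1% |
| 4 | 0.64 | 14% | 0.2% |
| 6 | 0.68 | 34% | 1.5% |

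Separate simulations at six predictors gave 35% and 36%, so about 35%.

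**Routes closer to the plan's reduction steps.** The assumption is 11 variables: six game metrics (four numeric, two binary) and five demographics collapsed to one term each. The latent correlation among game metrics was set at 0, 0.3, 0.5 and 0.7, with 3000 runs each, because the protocol gives no correlation.

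| Route | Correlation 0 | 0.3 | 0.5 | 0.7 |
|---|---|---|---|---|
| PCA on all 11: mean components kept | 5.1 | 4.4 | 4.0 | 3.7 |
| PCA on all 11: AUC ≥ 0.70 | 24% | 18% | 15% | 12% |
| Best two of 11 by correlation with group: AUC ≥ 0.70 | 30% | 24% | 22% | 20% |

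A repeat simulation gave 11–24% and 20–31%. Picking the best two from the data thus raises the chance from 3% (two fixed in advance) to 20–30%: a shorter model is not more reliable in this respect if the data chose it. If PCA were applied to the game metrics only and five demographics were added, about six to eight terms remain and the chance is 32–54%.

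**With some signal.** One real predictor with a true AUC of 0.70, among six: mean apparent AUC 0.76, mean AUC in new people 0.65, so optimism of 0.76 − 0.65 = 0.11. One grade step on the protocol's scale is 0.10.

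**What correction does.** Corrected AUC = apparent AUC − mean over resamples of (AUC of the resample model in its resample − AUC of that model in the original 58). For six null predictors (150 data sets, 100 resamples each), the mean falls from 0.68 to 0.56, and the share at 0.70 or above from 37% to 3%. In new data the same models average 0.50 and none reaches 0.70. Correction removes 0.68 − 0.56 = 0.12 of an optimism of 0.68 − 0.50 = 0.18, about two thirds.

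**The case against.** **RQ4 is a pilot and its shortfall is disclosed.** True, and this limits the harm: the foreseen next step is a larger study. But sections 3.3 and 3.11 concede only that the sample is small and the model less reliable. Neither says that the reported performance will be too high on average.

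**RQ4 asks about association, and ROC is a supporting check.** Also true. G3's own diagnostic accuracy is RQ3. The check is nonetheless planned, and its figures will be read.

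**Validation could sit in a statistical analysis plan.** It could, and ROC evaluation is compatible with optimism correction. The point rests on what the protocol does state: a data-based choice of predictors and an ROC evaluation, with no second sample.

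A reader might infer more than the text supports:

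- *That the chi-square tests are a screening step.* Section 3.9 gives no entry rule based on them.
- *That PCA and category merging bias the result as predictor choice does.* PCA with an eigenvalue cut-off does not use the outcome, and merging is not described as outcome-driven. The clearly data-based step is the choice of strongest predictors.
- *That all 11 variables enter the model.* That would give a null AUC of 0.70 or above in about 82% of runs, but it skips the protocol's own reduction steps.
- *That a model with no signal would often look excellent.* At six predictors an AUC of 0.80 or above occurs in under 2% of runs.
- *That the protocol itself grades RQ4 on the 0.7/0.8/0.9 scale.* The scale is stated under RQ3. It is the protocol's only AUC scale and is worded generally, so applying it to RQ4 is reasonable but inferred.

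**Conclusion.** The concern holds in a limited form. Followed as written, section 3.9 yields apparent values of AUC, sensitivity and specificity for RQ4, and these are biased upward. How often pure noise would reach 0.70 depends on how many terms remain and how they were chosen, which the protocol leaves open: from 3–7% for two or three predictors fixed in advance to about 35% for the six listed factors, with the data-driven routes described above in between on most readings.

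The conclusion assumes that the 58 participants are the only data used to evaluate the model, which follows from no other being named. The percentages assume normal independent predictors for the fixed counts, and one term per demographic variable in the 11-variable routes. Leaving education or living status uncollapsed would add terms and raise the rates; stronger correlation among game metrics with PCA on all variables lowers them. This should be corrected before analysis. It does not undermine the study's other aims.

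**What to change.** In section 3.9 (RQ4), after the sentence on model performance:

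- Report the bootstrap optimism-corrected AUC, sensitivity and specificity, with intervals, alongside the apparent values.
- Repeat the PCA retention and any outcome-based choice of predictors inside each resample.
- Fix the category merging beforehand, without reference to cognitive status. Judgement-based merging cannot be repeated within resamples.
- Apply any verbal AUC grade only to the corrected AUC, and say whether the scale given under RQ3 is meant for RQ4.
- State that some optimism remains: a null model with six predictors still averages about 0.56 after correction.

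The cost is a paragraph of text, a little extra code and a less favourable reported AUC. No participants or procedures are added.
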